9.2 Study Endpoints

Pharmacokinetics:

The primary endpoints for BE assessment will be comparison of AUC_{0-inf} and C_{max} of MMF between treatments. In addition, AUC_{0-t} will be compared between treatments.

Additional PK parameters AUC% extrapol, t_{max}, K_{el}, and t_{1/2} of MMF will be computed for information.

Safety:

Safety endpoints will include vital signs, clinical laboratory tests, and AEs.

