12.1 Pharmacokinetic Parameters

PK analysis of plasma concentration vs. time data of MMF will be performed using noncompartmental methods with the following parameters calculated as appropriate or data permitting:

AUC _{0-t} :	The area under the concentration-time curve, from time 0 (dosing time) to the last time point (t _{last}) with measurable drug concentration, as calculated by the linear trapezoidal method.
AUC _{0-inf} :	The area under the concentration-time curve from time 0 (dosing time) extrapolated to infinity. AUC _{0-inf} is calculated as the sum of AUC _{0-t} plus the ratio of the last measurable drug concentration to the apparent terminal first-order decay rate constant.
AUC%extrap:	Percent of AUC _{0-inf} extrapolated from the last time point with measurable drug concentration to infinity calculated as $(1 - AUC_{0-t}/AUC_{0-inf}) * 100$.
C _{max} :	Maximum observed drug concentration.
t _{max} :	Time to reach C _{max} . If the maximum value occurs at more than one time point, t _{max} is defined as the first time point with this value.
Kel:	Apparent terminal first-order decay rate constant calculated from a semi-log plot of the plasma concentration-time curve. The parameter will be calculated by linear least-squares regression analysis using at least 3 appropriate time points in the terminal log-linear phase.
t _{1/2} :	Apparent plasma half-life which will be calculated as $0.693/Kel$.

No value for Kel, AUC_{0-inf}, AUC%extrap, or t_{1/2} will be reported for cases that do not exhibit an apparent terminal log-linear phase in the concentration-time profile. No PK parameters will be calculated for subjects with 3 or fewer consecutive time points with detectable concentrations throughout the collection period.

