12.2 Statistical Methods

Detailed methodology for summary and statistical analyses of the data collected in this study will be documented in a Statistical Analysis Plan (SAP). The SAP will be prepared by Celerion and agreed upon with the Sponsor. This document may modify the plans outlined in the protocol; however, any major modifications of the primary endpoints definition and/or its analysis will also be reflected in a SAP amendment. Additional statistical analyses other than those described in this section may be performed if deemed appropriate and will be presented in the SAP and clinical study report.

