12.2.2 Subjects to Analyze

PK Population: Plasma samples from all subjects will be assayed even if the subjects do not complete the study. All subjects who comply sufficiently with the protocol and display an evaluable PK profile (e.g., exposure to treatment, availability and validity of measurements, and absence of major protocol violations) will be included in the PK analyses to determine PK parameters of MMF. Subjects who vomited within 5 hours after drug dosing may be excluded from the PK analyses.

Statistical Population: Statistical analysis will be performed on all subjects contributing to PK parameters of MFF (C_{max}, AUC_{0-inf}, and AUC_{0-t}). However, BE assessment will be primarily based on PK parameter data from subjects who complete the study or have sufficient data for a pairwise comparison, i.e., from both treatments.

Safety Population: All subjects who received at least one dose of the study drug will be included in the safety evaluations.

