12.2.4 Statistical Analysis

An ANOVA will be performed on the ln-transformed AUC_{0-t}, AUC_{0-inf}, and C_{max} using SAS[®] Proc Mixed. The ANOVA model will include sequence, treatment, and period as fixed effects, and subject nested within sequence as a random effect. Each ANOVA will include calculation of least-squares means (LSM) of the ln-transformed parameter as well as the LSM difference between treatments.

Ratios of geometric LSM (GLSM) will be calculated using the exponentiation of the difference between treatment LSM from the analyses on the ln-transformed AUC_{0-t}, AUC_{0-inf}, and C_{max}. These ratios will be expressed as a percentage, test relative to the reference (Treatment A vs. Treatment B).

Consistent with the two one-sided test, ⁶ 90% CIs for the GLSM ratios will be derived by exponentiation of the CIs obtained for the LSM difference between treatments resulting from the analyses on the ln-transformed AUC_{0-t}, AUC_{0-inf}, and C_{max}. The CIs will be expressed as a percentage, test relative to the reference (Treatment A vs. Treatment B).

Bioequivalence criteria will be met if the 90% CIs for the ratios of GLSMs of C_{max} and AUC_{0-inf} of MMF of the Test (Treatment A) to the Reference (Treatment B) fall within the limit of 80.00 and 125.00%.

Time to maximal drug concentration, t_{max}, will also be analyzed without transformation using a non-parametric method (Wilcoxon test). This analysis will only be performed for information purpose, not for BE assessment.

Additional details of statistical analysis methods will be included in the SAP.

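### Section 12.1 withholds Cmax, a co-primary endpoint, from sparse profiles although Cmax needs no terminal phase; if a test dose barely releases, this can favour a BE pass

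*Combined protocol and SAP*

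**What the plan says.** Section 12.1 has three provisions on sparse or incomplete profiles.

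- Kel is estimated "using at least 3 appropriate time points in the terminal log-linear phase".
- Of Kel, t1/2, AUC0-inf and AUC%extrap, none "will be reported for cases that do not exhibit an apparent terminal log-linear phase in the concentration-time profile".
- A wider rule follows: "No PK parameters will be calculated for subjects with 3 or fewer consecutive time points with detectable concentrations throughout the collection period". It has no exception for Cmax, which 12.1 defines simply as the highest observed concentration.

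Section 9.2 makes Cmax co-primary: "The primary endpoints for BE assessment will be comparison of AUC_{0-inf} and C_{max} of MMF between treatments". Section 12.2.4 sets the decision: "Bioequivalence criteria will be met if the 90% CIs for the ratios of GLSMs of C_{max} and AUC_{0-inf} of MMF" lie within 80.00–125.00%.

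Section 12.2.2 admits to the PK population subjects who "display an evaluable PK profile (e.g., exposure to treatment, availability and validity of measurements, and absence of major protocol violations"), and adds that "BE assessment will be primarily based on PK parameter data from subjects who complete the study or have sufficient data for a pairwise comparison", meaning data from both treatments.

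Section 12.2 defers detail: "Detailed methodology for summary and statistical analyses of the data collected in this study will be documented in a Statistical Analysis Plan (SAP"). It allows additional analyses but requires none. The text of that SAP is not in the supplied file.

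**The concern.** The first two provisions already deal with every parameter that depends on a terminal slope. What the wider rule mainly adds is the loss of Cmax, tmax and AUC0-t, and the trigger is the post-dose result itself.

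A capsule that releases almost nothing gives few detectable samples. Its low Cmax is what a BE comparison should register, yet under this rule the value may never be calculated, and the pairwise wording of 12.2.2 then takes the subject out of the primary comparison. Deleting a near-zero test profile favours a pass; deleting a reference profile can move the result either way. Section 8.2.1 says that effectiveness of the test product will be inferred from BE, so the Cmax decision carries weight.

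The unit of the rule is also unsettled. It speaks of subjects and of the whole collection period. Three readings are possible:

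1. One sparse period loses that period's parameters.
2. One sparse period removes the subject.
3. The count runs across both periods, so a subject with one normal profile is not caught at all.

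Under the first two the Cmax pair is lost; under the third it is kept.

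**Working it through.** **Inputs from the protocol.** Intra-subject CV 24%, true ratio 0.95–1.05, power at least 95%, 50 dosed including 6 spare (12.2.1); limits 80.00–125.00% (12.2.4); half-life about 1 h (8.1.1); sampling half-hourly to 8 h, then at 9, 10, 11, 12 and 24 h (section 6, footnote m).

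**Assumptions, not in the documents.** One test profile has its Cmax multiplied by a fraction f = 0.10, 0.05 or 0.02; the ratio in the other subjects is 0.95; sequences are equal in size; the LLOQ is high enough to trigger the rule.

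**1. The plan's own figure.** σ_w = √ln(1 + 0.24²) = 0.2366; SE = σ_w√(2/N); df = N − 2. Two one-sided tests at 5% and ratio 0.95 give 94.8% power at N = 42 and 95.6% at N = 44. So 44 + 6 = 50 reproduces. With 1, 2 or 3 of the 44 excluded, power is 95.2%, 94.8% or 94.3%. The sample size is sound; the issue is which profiles are removed.

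**2. One low test profile kept, n = 50.** The log estimate moves by ln(f)/50. The variance of the within-subject differences, 2σ_w² = 0.112, rises by about (ln f)² × (1 − 1/25)/48 = 0.02(ln f)². The 90% CI is estimate ± 1.677 × √(variance/50), with 48 df.

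- f = 0.10: estimate 0.95 × e^(−2.303/50) = 0.907; variance 0.112 + 0.106 = 0.218; half-width 0.111; CI 0.812–1.014.
- f = 0.05: estimate 0.895; variance 0.112 + 0.179 = 0.291; half-width 0.128; CI 0.787–1.017.
- f = 0.02: estimate 0.879; variance 0.112 + 0.306 = 0.418; half-width 0.153; CI 0.754–1.024.

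These agree with the simulated medians (0.813–1.013, 0.787–1.017, 0.754–1.024). With the profile deleted the median CI is 0.877–1.029.

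**3. Probability of passing on Cmax** (simulation, 100,000 runs per case; rank-based column 3,000 runs).

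| f | Kept | Shift in estimate only | Rank-based CI, kept | Deleted |
|---|---|---|---|---|
| 0.10 | 63% | 84% | 93% | 97% |
| 0.05 | 37% | 75% | 93% | 97% |
| 0.02 | 11% | 62% | 92% | 97% |

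At f = 0.10 the loss is 97 − 63 = 34 points, of which 97 − 84 = 13 come from the shift and the other 21 from CI widening. Widening is more than half in all three cases. With 44 evaluable the kept figures are 48%, 23% and 4%, against 95% deleted. A near-zero reference profile, n = 50, gives 98%, 95% or 79% kept against 97% deleted.

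**4. When the rule is triggered.** Four half-hourly samples span 1.5 h, over which a 1-h half-life lowers concentration by a factor of 2^1.5 = 2.83. Below an LLOQ of about f/2.83, four samples from the peak onward stay detectable and the rule does not apply. A one-compartment model (absorption rate 1–4 per h, lag 0.5–4 h) sets the upper end. The trigger thresholds are about 3.5–8.3%, 1.8–4.1% and 0.7–1.7% of typical Cmax for f = 0.10, 0.05 and 0.02. At an LLOQ of 0.5–2%, f = 0.10 leaves 6–14 detectable points and f = 0.05 leaves 4–12, so neither triggers. At f = 0.02 the rule starts to trigger at an LLOQ of about 1%; at 2%, none or one point remains.

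**5. Late profiles.** A profile first detectable at 10 h or later and undetectable at 24 h has at most three detectable points (10, 11 and 12 h). Modelled observed Cmax is 46–100% of typical, and the pass probability is 94–97% kept against 97% deleted.

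**The case against.** The rule is fixed in advance and worded identically for both treatments. All samples are assayed (12.2.2) and concentrations are summarised (12.2.3), so a failed profile would not be hidden. The SAP, which was not supplied, may contain the missing analysis. Most of the computed loss is one extreme log value inflating the ANOVA variance, and a rank-based interval on the same data still passes 92–93% of the time. The larger figures need a fairly insensitive assay, and under the subject-level reading nothing is deleted. All of this stands, and it limits the point to a rare event.

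It does not remove the point. Identical wording does not mean identical effect when a low profile sits on the test arm. Nothing supplied requires an analysis that keeps such a profile, and the rule is written so that its Cmax need not exist. If the SAP already has that analysis, the sponsor can point to it.

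A reader might go further and infer that the rule will delete failed test doses in this trial, or that it hides late release. The documents support neither. They give no LLOQ or failure rate. A near-zero test profile would need both 95 mg capsules to fail; one failing (f about 0.5) gives 94% kept and is unlikely to trigger the rule. A first detection at 10 h is four times the 2.5 h median reference tmax implied by 10.3.3, and late profiles barely move the BE criterion.

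**Conclusion.** The point holds as a low-frequency risk to the Cmax decision from a single profile. Section 12.1 states an outcome-dependent exclusion of a co-primary endpoint that needs no terminal phase, and the supplied text requires no analysis showing whether the conclusion depends on it.

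If one near-zero test profile occurred and were deleted, the chance of passing on Cmax would be 97% instead of 63%, 37% or 11%. This rests on CV 24%, ratio 0.95, 50 subjects, the assumed f, an LLOQ in the triggering range but below the profile's own peak (otherwise there is no Cmax to keep), and a reading of the rule that removes the period or the subject. It is a reason to change the wording, not evidence of bias. It casts no doubt on the sample size, and it cannot be taken to mean that the SAP lacks the analysis.

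**What to change.** - **12.1:** apply the minimum-points rule by treatment period, and only to Kel, t1/2, AUC0-inf and AUC%extrap. Calculate Cmax and tmax for any profile with at least one quantifiable concentration. Report AUC0-t for sparse profiles with a flag rather than excluding it, since a further exclusion would again depend on the result.
- **12.2.2:** state that a sparse profile alone does not make a period non-evaluable for Cmax.
- **12.2.4 or the SAP:** list sparse and all-BLQ profiles by treatment. Prespecify the Cmax BE analysis with and without the sparse profiles, naming the primary one before concentrations are known. All-BLQ profiles have no logarithm to analyse and can only be listed.

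The BE criterion stays as written. The cost is wording only, with no new subjects or samples. The downside is that a BE pass may look less robust if a dose fails to release, because one extreme log value widens the ANOVA interval. A rank-based interval beside it would show how much of the change is widening.

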12.2 Statistical Methods

Detailed methodology for summary and statistical analyses of the data collected in this study will be documented in a Statistical Analysis Plan (SAP). The SAP will be prepared by Celerion and agreed upon with the Sponsor. This document may modify the plans outlined in the protocol; however, any major modifications of the primary endpoints definition and/or its analysis will also be reflected in a SAP amendment. Additional statistical analyses other than those described in this section may be performed if deemed appropriate and will be presented in the SAP and clinical study report.

12.2.1 Determination of Sample Size

The sample size was calculated⁵ using a power of at least 95% and an alpha error of 5%. The power was defined as the probability of having a 90% CI to a Test/Reference ratio within the acceptance criteria of 80.00 - 125.00%. A true ratio between 95 - 105% was assumed and an intra-subject CV of 24% was used. A total of 50 subjects will be dosed. This includes 6 additional subjects to account for possible dropouts or non-evaluable data.

12.2.2 Subjects to Analyze

PK Population: Plasma samples from all subjects will be assayed even if the subjects do not complete the study. All subjects who comply sufficiently with the protocol and display an evaluable PK profile (e.g., exposure to treatment, availability and validity of measurements, and absence of major protocol violations) will be included in the PK analyses to determine PK parameters of MMF. Subjects who vomited within 5 hours after drug dosing may be excluded from the PK analyses.

Statistical Population: Statistical analysis will be performed on all subjects contributing to PK parameters of MFF (C_{max}, AUC_{0-inf}, and AUC_{0-t}). However, BE assessment will be primarily based on PK parameter data from subjects who complete the study or have sufficient data for a pairwise comparison, i.e., from both treatments.

Safety Population: All subjects who received at least one dose of the study drug will be included in the safety evaluations.

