10.3.3 Early Termination of Subjects from the Study

Subjects are free to withdraw from the study at any time for any reason.

In addition, subjects may be withdrawn from the study by the investigator or designee for the following reasons:

- AEs.
- Difficulties in blood collection.

A subject may be withdrawn by the investigator (or designee) or the Sponsor if enrollment into the study is inappropriate, the study plan is violated, or for administrative and/or other safety reasons.

If a subject vomits within 5 hours after dosing, i.e., a period equal to two times the median t_{max} of MMF after administration of the reference product, he/she may be withdrawn from the study.

The clinical report will include reasons for subject withdrawals as well as details relevant to the subject's withdrawal.

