10.5.3 Blinding

This is an open-label study.

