11.3 Pharmacokinetic Assessments

11.3.1 Blood Sampling and Processing

For all subjects, blood samples for the determination of MMF will be collected in prechilled blood collection tubes containing sodium fluoride/potassium oxalate as the stabilizer and anticoagulant, respectively at scheduled time points as delineated in the Study Events Flow Chart ([Section 6](#)) by direct venipuncture using a disposable sterile needle at each time of collection.

Blood collection tubes will be placed in an ice bath at least 5 minutes prior to blood collection. Immediately upon blood collection, the collection tubes will be gently inverted

8-10 times to allow mixing with the anticoagulant and the stabilizer, and will be cooled in an ice bath and centrifuged (approximately at 2056 x gravity for 7 minutes) under refrigeration at a temperature of approximately 4°C as soon as possible and no later than 60 minutes upon collection. Plasma samples will be divided into 4 aliquots and stored in suitably labeled polypropylene tubes which are prechilled and contain pre-aliquoted an appropriate volume (100 µL per 1 mL of plasma) of the 10% (v/v) phosphoric acid solution in each tube as a stabilizer. The storage tubes will be labeled, at a minimum, with Sponsor company, protocol number, subject number, sample matrix, study period, study day, scheduled sample time and tube number (eg., #1, #2, #3, #4). Tubes will be stored in an upright position in a non-self-defrosting freezer with the temperature maintained at approximately -70°C or lower until shipment to the designated bioanalytical laboratory where samples will be stored at approximately -70°C or lower. Samples should be placed into the freezer within 90 minutes of blood collection.

At the end of the study, the first aliquot (Aliquot #1) of each plasma sample will be shipped together to the Sponsor's designated bioanalytical laboratory; while the second aliquot (Aliquot #2) will be sent after receipt in good condition of the previous shipment. The other aliquots of each sample will be retained at the CRU until further instruction for shipment.

Additional instruction for blood sampling, collection, processing, and sample shipment will be provided separately.

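### Does optional exclusion of subjects who vomit within 5 hours leave the primary bioequivalence set open to choice?

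*Combined protocol and SAP*

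**What the plan says.** Section 12.2.2 (Subjects to Analyze) admits to the PK analyses subjects who comply sufficiently and have an evaluable profile, and adds: "Subjects who vomited within 5 hours after drug dosing may be excluded from the PK analyses". The same section states: "Plasma samples from all subjects will be assayed even if the subjects do not complete the study". For the primary comparison it says that "BE assessment will be primarily based on PK parameter data from subjects who complete the study or have sufficient data for a pairwise comparison", meaning data from both treatments.

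Section 10.3.3 uses the same window for withdrawal from the study and gives its basis: "If a subject vomits within 5 hours after dosing, i.e., a period equal to two times the median" tmax of the reference product. That wording is also permissive.

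Section 12.1 has a separate, data-based rule: "No PK parameters will be calculated for subjects with 3 or fewer consecutive time points with detectable concentrations throughout the collection period".

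Three other places bear on timing and control. Section 10.5.3 reads "This is an open-label study". Section 11.3.1 says "At the end of the study, the first aliquot (Aliquot #1) of each plasma sample will be shipped together" to the bioanalytical laboratory. Section 12.2.4 ends with "Additional details of statistical analysis methods will be included in the SAP", and Section 12.2 says that the CRO prepares the SAP in agreement with the sponsor. No separate SAP text is in the file.

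**The concern.** The window is exact but its consequence is optional. Section 12.2.2 names no decision-maker, gives no criterion beyond the window and general evaluability, and sets no deadline relative to the assay. Treatment is known to all, and the vomiter's samples are assayed in any case. A vomiter who completes both periods meets the pairwise requirement, so that one permissive word decides whether the pair enters the analysis of Cmax and AUC0-inf.

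If the choice were made with concentrations in hand, the false-pass rate could not be lower than under either fixed rule. In the other direction, keeping a subject who lost much of a Test dose could fail a product that meets the plan's own assumptions. Section 8.2.1 infers effectiveness from bioequivalence, so a primary set that is not fully determined deserves a check.

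**Working it through.** **What the text already fixes.** The 5-hour window is the same in Sections 10.3.3 and 12.2.2 (twice the median tmax, so the implied median is 5/2 = 2.5 h). Section 11.2.5.3 requires the date and time of onset of each adverse event, so who vomited inside the window is known without the assay. Samples ship at the end of the study, so any withdrawal under Section 10.3.3 during conduct comes before any concentration exists. A subject withdrawn in Period 1 has no pair and falls outside the primary comparison. The discretion therefore concerns only vomiters who stay in the study or who vomit in Period 2.

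**The plan's own figure.** Inputs from Section 12.2.1: CV 24%, true ratio 0.95 to 1.05, limits 0.80 to 1.25, 90% CI, power at least 95%, 50 dosed including 6 spare.

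- σ_w = √ln(1 + 0.24²) = 0.2366; SE = σ_w·√(2/n); df = n − 2.
- At ratio 0.95, two one-sided tests need n = 44 (power 95.6%), which matches 50 − 6 = 44. Power is 96.9% at 48 and 97.3% at 50.

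The sample size reproduces, and it absorbs a few exclusions.

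**Effect of one vomiter.** Assumed, because the documents give neither: one vomiter, with a fraction f of exposure remaining in the affected period. If the subject is kept, the estimated T/R ratio is multiplied by f^(1/50) for a Test vomiter and divided by it for a Reference vomiter. For f = 0.5 the factor is 0.5^(1/50) = 0.986, so a true 0.95 is estimated around 0.95 × 0.986 = 0.937.

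The 2×2 crossover was simulated on the ln scale for one parameter (N = 50, 100,000 trials per scenario, Monte Carlo SE at most 0.16 points). Free choice means a pass if either set passes on the same data.

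| Scenario | f = 80% | 50% | 20% | 10% |
|---|---|---|---|---|
| True 0.95, Test vomiter kept: pass | 96.7% | 94.3% | 82.0% | 62.4% |
| Same, excluded: pass | 97.1% | 97.1% | 97.1% | 97.1% |
| Same, the two sets disagree | 0.9% | 2.9% | 15.2% | 34.7% |
| True 0.80, one Reference vomiter, always kept: false pass | 6.0% | 7.7% | 9.5% | 9.1% |
| Same, free choice: false pass | 6.2% | 7.7% | 9.5% | 9.1% |
| True 0.80, two Reference vomiters, always kept: false pass | 7.1% | 11.5% | 17.6% | 18.8% |
| Same, free choice: false pass | 7.4% | 11.5% | 17.6% | 18.8% |

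Fixed exclusion gives about 5.0% in the false-pass scenarios. A Test vomiter at a true ratio of 1.25 mirrors the Reference vomiter at 0.80, with free choice at 6.1/7.7/9.5/9.2%.

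**What discretion itself adds.** Free choice minus always kept is 6.2 − 6.0 = 0.2 points and 7.4 − 7.1 = 0.3 points at f = 80%, and nothing to one decimal at 50% or below. A kept Reference vomiter pulls the estimate away from 0.80, so the kept set passes almost whenever the excluded set does. The largest increment found is with one Test and one Reference vomiter at f = 80%: 5.8% under free choice against about 5.0% under the worse fixed rule, or 0.8 points.

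At true ratio 0.95 the disagreement also runs mostly one way once the loss is large: 97.1 − 82.0 = 15.1 points of lost power against 15.2% disagreement at f = 20%, and 97.1 − 62.4 = 34.7 against 34.7% at f = 10%. Almost always the set without the vomiter passes, and that is the correct verdict for a product at 0.95.

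**What mandatory exclusion would give.** It holds about 5% only if vomiting is unrelated to the subject's own T/R ratio. In an illustrative extreme, where the vomiter is the subject with the highest Reference exposure in a sequence (between-subject CV 0 to 50%), fixed exclusion itself gives 6.0% to 7.9% false passes with one vomiter and 7.1% to 11.6% with two.

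**The case for a change.** The best case for a change is that a primary set should be fixed before results exist, and that doing so costs one sentence and a dated list. Nothing in the supplied text requires it. The SAP has no stated deadline relative to the assay, and Section 12.2.2 does not refer the emesis decision to it. Against fixed exclusion, free choice does raise false passes, to as much as 9.5% with one Reference vomiter and about 19% with two. In the extreme case of dependent vomiting, free choice is also worse than fixed exclusion: 6.8% to 13.8% against 6.0% to 7.9% with one vomiter.

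Part of this stands. The wording is open, and a dated list of exclusions before concentrations are released would be good practice. But with vomiting unrelated to the ratio, a fully prespecified rule of always keeping the subject has nearly the same false-pass rate, so the figures mainly measure keeping against dropping. They do not show that the choice between those two rules is settled: dropping loses judgement over late emesis with little exposure lost, and it has its own excess when vomiting tracks exposure. The larger figures also need several vomiters or a severe loss. Section 8.1.1 does not list vomiting among the most common reactions to the reference product.

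**Conclusion.** The reading of Section 12.2.2 is correct, but the point is missing detail of a kind that analysts ordinarily settle in the SAP or at population review, using the stated 5-hour window, the recorded onset time and the evaluability criteria. The supplied text does not show that the SAP leaves it open, or that anyone would decide with results in hand.

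With one vomiter keeping at least half of the exposure, inclusion costs 97.1 − 94.3 = 2.8 points of power or less at ratio 0.95 and gives up to 7.7% false passes at the limit. Freedom to choose adds at most about 0.8 points beyond the worse fixed rule in the scenarios with vomiting unrelated to the ratio.

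These sizes rest on assumed vomiter counts and exposure losses, CV 24%, N = 50 and one parameter. Section 12.2.4 requires both Cmax and AUC0-inf to pass. If both are truly at 0.80 (assumed correlation 0.5 to 0.95), free choice with one Reference vomiter gives 1.6% to 7.3%; if only one is at the limit (correlation 0.8), it gives 6.1% to 9.6%. No change to the plan is called for.
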